4.6 Demographic and Other Baseline Characteristics

Demographics to be summarized will include:

- Age (years)
- Assigned Sex at Birth (Female, Male)
- Race (American Indian or Alaska Native, Asian, Black or African American, Native Hawaiian or Other Pacific Islander, White) with Subcategories (as collected on the CRF).
- Ethnicity (Hispanic or Latino, Not Hispanic or Latino, Not Reported, Unknown)
- Country
- Childbearing Potential (Yes, No)

Baseline characteristics will include:

- Height (cm)

- Weight (kg)
- Body mass index (BMI) (kg/m²)
- Target Lesions at Baseline (Yes, No)
- Non-target Lesions at Baseline (Yes, No)
- Measurable Disease at Baseline (Yes, No)

Disease History at Baseline and Cancer History will also be summarized.

Summaries of demographic and other baseline characteristics will be produced by line of therapy in the Safety Analysis Set.

A by-participant listing of demographic and baseline characteristics will be produced including participant identifiers, demographic and baseline variables, and line of therapy .

Age will be calculated as the number of complete years between a participant's birth date and the date of informed consent.

4.7 Prior and Concomitant Medications and Procedures

Medication start and stop dates will be compared to the date of first dose of study medication to allow medications to be classified as either Prior only, both Prior and Concomitant, or Concomitant only. Medications starting after the completion/withdrawal date will be listed but will not be classified or summarized.

Medications that start and stop prior to the date of first dose of study medication will be classified as Prior only. If a medication starts before the date of first dose of study medication and stops on or after the date of first dose of study medication, then the medication will be classified as both Prior and Concomitant. Medications will be classified as Concomitant only if they have a start date on or after the date of first dose of study medication.

If medication start and/or stop dates are missing or partial, the dates will be compared as far as possible with the date of first dose of study medication. Medications will be assumed to be Concomitant only, unless there is clear evidence (through comparison of partial dates) to suggest that the medication started prior to the first dose of study medication. If there is clear evidence to suggest that the medication started prior to the first dose of study medication, the medication will be assumed to be both Prior and Concomitant, unless there is clear evidence to suggest that the medication stopped prior to the first dose of study medication. If there is clear evidence to suggest that the medication stopped prior to the first dose of study medication, the medication will be assumed to be Prior only.

Procedure dates will be compared to the date of first dose of study medication to allow medications to be classified as Prior or Concomitant.

Partial or missing dates will be imputed per rules outlined in [Appendix 6.2](#).

All prior and concomitant medications/procedures will be coded using the latest version of WHO Drug Dictionary (WHO-DD) version (March 1, 2021 or higher).

Summaries will be produced of the number and proportion of participants with any prior and concomitant medications/procedures and for specific medications, including Anatomic Therapeutic Chemical (ATC) class 2 and preferred term (PT) by line of therapy. Participants taking more than one medication or having more than one procedure within the same ATC class 2 and PT will only be counted once.

By-participant listings of prior and concomitant medications will be produced with ATC level 2 and preferred term, including actual non-imputed start/stop dates, route, dose, frequency, and indication (Analysis Set: Safety Analysis Set). When the indication is an AE or medical history, the medical history or AE identifier will be listed.

By-participant listings of prior and concomitant procedures will be produced with ATC level 2 and preferred term, including procedure date(s), site, type of procedure, if oncological in nature, and if used to treat target or non-target lesions.

4.7.1 Subsequent Antineoplastic Cancer Therapy

Subsequent antineoplastic cancer therapy will be summarized.

A by-participant listing for subsequent antineoplastic cancer therapy will be produced.

4.8 Treatment Compliance

IMP and non-IMP treatment exposure/compliance will be monitored through dosing diaries in the eCRFs.

For each participant, dates of administration for each treatment are recorded on the corresponding Study Drug Administration eCRF forms. The start date of administration for the first entry will be considered the date of first dose of treatment, and the end date of administration for the last entry will be considered the last date of treatment.

If the date of last dose of study treatment is missing, ie, participant lost to follow-up, the last known drug administration date will be used to calculate duration of exposure.

Compliance with IMP and non-IMP treatments will be summarized.

For oral treatments (Lerociclib, Letrozole) and injection treatment (Fulvestrant), the compliance percentage will be summarized as:

$$[\text{Total Dose (mg) Taken} / \text{Total of All Planned Doses (mg)}] * 100$$

Planned doses will account for any prescribed dose interruptions and modifications. Treatment compliance will be summarized for each treatment individually.

Compliance for injected treatment Goserelin cannot be calculated, as this is an implant that gradually releases total dose injected.

The number and percentage of participants who had at least one dose interruption will be provided. The number and percentage of participants with < 80%, 80% to 120%, and > 120% compliance will be provided by line of therapy for each visit. For all other compliance variables, compliance will be summarized by percentage for the whole exposure period.

The compliance variables will be listed in a by-participant listing.

4.9 Safety Evaluation

All safety summaries and analyses will be based upon the Safety Analysis Set as defined in [Section 4.5](#).

4.9.1 Adverse Events

4.9.1.1 Definition of Adverse Event

An adverse event (AE) is any untoward medical occurrence in a clinical study participant, temporally associated with the use of a study intervention, whether considered related to the study intervention or not. See Appendix 3 of the protocol for full details of AE definition and classification.

4.9.1.2 Coding of Adverse Events

AEs will be coded using the Medical Dictionary for Regulatory Activities (MedDRA) Version 23.0 or higher. AE severity will be graded using NCI CTCAE v5.0.

4.9.1.3 Treatment-emergent Adverse Events (TEAEs)

Treatment-emergent adverse events (TEAEs) will be tabulated and are defined as those adverse events that either start or worsen in severity on or after the date/time of first dose of study treatment through 30 days after end of treatment or the day before initiation of a new antineoplastic treatment, whichever occurs first. Where dates are missing or partially missing, AEs will be assumed to be treatment-emergent, unless there is clear evidence (through comparison of partial dates) to suggest that the adverse event started prior to the first dose of study treatment or after the Post-Treatment Follow-up visit. Partial dates will be imputed per rules outlined in [Appendix 6.2](#).

An overall summary table will be created to present high level TEAE and treatment-related adverse event (TRAE) information. The following will be summarized (presenting the number of participants and number of events) by line of therapy, system organ class (SOC), and preferred term (PT):

- TEAEs
- TRAEs
- Serious TEAEs
- Serious TRAEs
- For each study treatment
 - TEAEs Leading to Drug Discontinuation
 - TEAEs Leading to Drug Reduction
 - TEAEs Leading to Drug Interruption
 - TEAEs Leading to Drug Reduction or Interruption

Additionally, the following summaries presenting the number of participants and number of events will also be created:

- TEAEs by line of therapy and PT
- TEAEs in >10% of participants by line of therapy and PT
- TRAEs by line of therapy and PT
- TEAEs by line of therapy, maximum severity grade, SOC, and PT (number of participants only)

Adverse event summaries will be ordered alphabetically for SOC, and decreasing frequency of PT within SOC for the total column (including both lines of therapy).

For each participant and each adverse event, the worst severity recorded will be attributed and used in the by-severity summaries. Similarly, the worst causality (most related to Lerociclib) will be attributed and used in the by-causality summaries. If severity or causality is missing, a conservative approach for AE assessment (implementing the worst case) will be followed.

Adverse events of special interest (AESIs) TEAEs and TRAEs will also be summarized by line of therapy, maximum severity grade, SOC, and PT for the following terms:

| AESI | Definition |
|---------------------------|-----------------------|
| Febrile neutropenia | MedDRA code #10016288 |
| Pneumonitis | MedDRA code #10035742 |
| Interstitial lung disease | MedDRA code #10022611 |

Note that if the PT or MedDRA code for any of these AESIs change in subsequent versions of MedDRA, this will not be considered a change to planned analysis.

By-participant listings of all TEAEs and serious TEAEs will be provided. These listings will be presented by line of therapy and will include center, participant identifier, age, sex, race, adverse event (SOC, PT, and verbatim term), date of onset, date of resolution, duration, severity, seriousness, outcome, action taken (each treatment), and causality (each treatment).

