| Risk of excess radiation exposure due to CT scans. | CT scans have been shown to result in complications from excess radiation exposure. | CT scans will be conducted every 8 weeks for the first 12 months of the study, and are then spaced out to every 12 weeks to mitigate radiation exposure. |
| Other | | |
| Risk of arthralgia due to letrozole/fulvestrant/goserelin. | Letrozole/fulvestrant/goserelin have been shown to result in arthralgia in patients with mBC. | Each participant will be provided with information about signs and symptoms of arthralgia, hot flushes, and fatigue during the consent process; instructions on when to contact a healthcare provider; and relevant contact information. |
| Risk of hot flushes due to letrozole/fulvestrant/goserelin. | Letrozole/fulvestrant/goserelin have been shown to result in hot flush in patients with mBC. | |
| Risk of fatigue due to letrozole/fulvestrant/goserelin. | Letrozole/fulvestrant/goserelin have been shown to result in fatigue in patients with mBC. | |

CDK = cyclin-dependent kinase; CT = computed tomography; DSUR = development safety update report; G-CSF = granulocyte colony-stimulating factor; IB = Investigator's Brochure; ILD = interstitial lung disease; mBC = metastatic breast cancer; TEAE = treatment-emergent adverse event.

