9.3.2.1. Analysis of Adverse Events

Adverse event data will be coded by SOC and PT using the current version of the MedDRA. The number and percentage of participants experiencing any TEAE and serious TEAE, overall, and by SOC and PT will be tabulated. Treatment-emergent AEs will also be summarized by severity grade (as assessed by the Investigator per NCI CTCAE v5.0).

Treatment-emergent AEs and SAEs related to treatment (ie, study intervention) will be further summarized by the treatment to which each is attributed (eg, lerociclib, letrozole, fulvestrant, or goserelin). Withdrawals due to AEs will be summarized.

Duration of AEs will be determined and included in the listings, along with action taken and outcome. Adverse events leading to treatment discontinuation will also be listed.

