| 
• The Investigator will assess the relationship between study intervention and the occurrence of each AE. The Investigator's assessment of the relationship of each AE to study intervention will be recorded in the source documents and the eCRF. Alternative causes, such as medical history, concomitant therapy, other risk factors, and the temporal relationship of the event to study intervention, should be considered and investigated, if appropriate. The following definitions are general guidelines to help assign grade of attribution: |
| 
– Not related: The event is clearly related to other factors, such as the participant's environment or clinical state, therapeutic interventions, or concomitant drugs administered to the participant. This is especially so when an event occurs prior to the commencement of treatment with the study intervention.– Unlikely related: The temporal association, participant history, and/or circumstances are such that study intervention is not likely to have had an association with the observed event. Other conditions, including concurrent illness, progression, or expression of the disease state, or reaction to a concomitant drug administered appear to explain the event.– Possibly related: The event follows a reasonable temporal sequence from the time of study intervention administration or follows a known response to the study intervention but could have been produced by other factors, such as the participant's clinical state, other therapeutic interventions, or concomitant drugs administered to the participant.– Probably related: The event follows a reasonable temporal sequence from the time of study intervention administration and follows a known response to the study intervention and cannot be reasonably explained by other factors, such as the participant's clinical state, other therapeutic interventions, or concomitant drugs administered to the participant.– Definitely related: The event follows a reasonable temporal sequence from the time of study intervention administration or control abates upon discontinuation or cannot be explained by known characteristics of the participant's clinical state. |

Follow-up of AEs and SAEs

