4.13 Changes in the Conduct of the Study or Planned Analysis

This SAP is based on the Study EQ132-201 protocol Version 3.0, Amendment 3, dated February 27, 2023. This amendment is considered substantial, based on the criteria set forth in Article 10(a) of Directive 2001/20/EC of the European Parliament and the Council of the European Union. However, it does not significantly impact analysis endpoints or methodology.

In addition, no changes to the statistical methods detailed in the study protocol have been implemented in this document.

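### The SAP omits the protocol's summary of related adverse events by attributed drug, keys its only causality rule to lerociclib, and declares no departure from the protocol

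*SAP*

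**What the plan says.** Protocol 9.3.2.1 (Analysis of Adverse Events) provides for tables of TEAEs and serious TEAEs. It then says that those related to treatment, which it explains as study intervention, "will be further summarized by the treatment to which each is attributed (eg, lerociclib, letrozole, fulvestrant, or goserelin").

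SAP 4.9.1.3 states: "An overall summary table will be created to present high level TEAE and treatment-related adverse event (TRAE) information". It lists TRAEs and serious TRAEs by line, system organ class and preferred term, a TRAE table by line and preferred term, and TRAE tables for the events of special interest. One bullet is broken out for each study treatment. It covers TEAEs leading to discontinuation, reduction, interruption, or reduction or interruption.

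On causality, the section has one rule for repeated events: "the worst causality (most related to Lerociclib) will be attributed and used in the by-causality summaries". Missing causality takes the worst case, with no drug named. The by-participant listings of TEAEs and serious TEAEs include "action taken (each treatment), and causality (each treatment").

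SAP 4.13 states that "no changes to the statistical methods detailed in the study protocol have been implemented in this document".

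**The concern.** The study has one arm and no comparator. Every participant takes lerociclib with letrozole or fulvestrant, and some also take goserelin. An all-cause table describes the combination and cannot show which component investigators held responsible. The protocol treats that question as relevant. Its risk table (Protocol 2.3.2) says that "Letrozole/fulvestrant/goserelin have been shown to result in arthralgia in patients with mBC", with parallel entries for hot flushes and fatigue. Fatigue is also among the toxicities anticipated in this study (Protocol 2.3), so at least one common symptom has more than one plausible source.

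The by-drug summary in Protocol 9.3.2.1 is the analysis the protocol specifies for this. If the SAP is followed as written, the summary is not produced, and nothing in the SAP tells the reader of the study report that it was dropped.

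**Working it through.** No arithmetic in either document bears on this point, so the check compares the texts.

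**1. What the protocol requires.** Two event classes (related TEAEs and related SAEs) for four named drugs: 2 × 4 = 8 by-drug summaries, each shown by line of therapy. The reference set is study intervention, not lerociclib alone.

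**2. What the SAP tabulates.**

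| Item | Protocol 9.3.2.1 | SAP 4.9.1.3 |
|---|---|---|
| Related events overall | Yes, to study intervention | TRAE and serious TRAE tables; drug scope not stated |
| Related events by attributed drug | Yes, four drugs named | No table |
| By-treatment tables | By attribution | By action taken |
| Causality to each drug | Summarized | Listed only |

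**3. Whether the SAP's TRAE tables could fill the gap.** That depends on what a TRAE is, and the SAP only expands the abbreviation.
- If it means related to any study treatment, as the protocol's gloss suggests, the SAP delivers the overall tables and 0 of the 8 by-drug summaries.
- If it means related to lerociclib, as the wording of the worst-causality rule might suggest to a programmer, the SAP delivers 2 of the 8 (lerociclib, both event classes), and the overall study-intervention tables are then missing.

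Neither reading meets Protocol 9.3.2.1.

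**4. Whether the by-treatment tables could fill it.** They record what was done to a drug, not what was thought to have caused the event. Protocol 6.5.2 does not allow dose modification of letrozole, fulvestrant or goserelin. If the protocol is followed, the reduction rows for those drugs should be empty whatever the attribution.

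**5. The worst-causality rule.** It is stated for by-causality summaries, and SAP 4.9.1.3 lists no table by causality grade. It is therefore the section's only guidance on resolving several causality ratings, it names one drug, and it does not match the protocol's study-intervention scope.

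**6. The causality cut-off.** SAP 4.9.1.1 refers to Protocol Appendix 3 for classification. That appendix introduces its scale with "The following definitions are general guidelines to help assign grade of attribution" and gives five grades, from not related to definitely related. Neither document says which grades make an event treatment-related.

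**7. Declared changes.** SAP 4.13 declares none, so the omission is not a documented decision.

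**The case against.** The strongest reply is that little of substance is at risk. The primary endpoint is the incidence of AEs and SAEs whatever their cause, and the TEAE and serious TEAE tables that deliver it are fully specified. That stands. A reader might infer that the primary analysis is ambiguous; it is not, because no all-cause count depends on attribution.

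Second, the protocol governs, and its gloss makes any study treatment the natural scope for a TRAE. This largely settles the scope of the overall tables, but it does not create the by-drug ones.

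Third, nothing is lost from the data. A reader might infer that the lerociclib-keyed rule erases attributions to the endocrine drugs. The documents do not support that: the rule is tied to by-causality summaries that are not listed, the TRAE tables count events as well as participants, and the listings keep causality to each treatment. Still, a listing is not the summary that the protocol specifies.

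Fourth, the time window for TRAEs might look open because the SAP does not restate it. It is not open: Protocol 9.3.2.1 speaks of treatment-emergent events, and the SAP plans TRAEs inside its TEAE section. Nor does the protocol's remark that "Duration of AEs will be determined and included in the listings, along with action taken and outcome" promise a listing of every collected AE.

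Fifth, Appendix 3 describes the unlikely grade as a probable absence of association, so counting possibly, probably and definitely as related is the obvious reading. Agreed. On its own, the missing cut-off is a detail to fill in.

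**Conclusion.** The point holds as a mismatch between protocol and SAP in supportive safety tables. A protocol-specified summary is absent, the only causality rule has a narrower drug scope than the protocol, and SAP 4.13 is wrong to report no change. The shortfall is all 8 by-drug summaries on the any-treatment reading of a TRAE, or 6 of 8 on the lerociclib reading.

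No shift in percentage points can be claimed. Neither document gives attribution rates, so any figure for how far a TRAE row would move would rest on assumed frequencies. Primary-endpoint incidence, the TEAE window and the sample size justification are unaffected. The correction is worth making because the study has no comparator and the protocol chose attribution by drug as its tabulated way to show the components separately, however imperfect that is.

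**What to change.** Keep the TEAE definition and window. In SAP 4.9.1.3, add text to this effect:

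*A TRAE is a TEAE rated possibly, probably or definitely related to at least one study treatment; missing causality counts as related. TRAEs and serious TRAEs will be summarized by line of therapy for any study treatment, and separately for lerociclib, letrozole, fulvestrant and goserelin among participants who received that drug. Worst causality is taken across all study treatments in the any-treatment tables, and for the named drug in the drug-specific tables.*

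The last sentence replaces the lerociclib-only rule. If the sponsor prefers not to produce the by-drug tables, SAP 4.13 should state and justify the departure, and the definition is still needed.

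The cost is one paragraph and up to eight further tables (four drugs, two event classes), which could be columns of existing ones. No new data are needed, since causality to each treatment is already planned for the listings. The drawbacks are more output, attribution that is subjective in an open-label study, and possibly small denominators for goserelin, which only pre- or perimenopausal women and men receive.

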4.9.2 Deaths

TEAEs resulting in death will be summarized by line of therapy, SOC, and PT.

Deaths will also be summarized by the number of deaths occurring in each line of therapy along with primary cause of death.

A listing of all deaths occurring during the study will be provided and will include center, participant identifier, age, sex, race, date of first treatment, date of last treatment, primary cause of death, on-treatment death (Yes/No), and autopsy performed (Yes/No).

4.9.3 Clinical Laboratory Evaluation

Chemical laboratory assessments include hematology, clinical chemistry, routine urinalysis, and pregnancy testing. The laboratory tests required by the protocol are detailed in Appendix 10.2 of the protocol.

All laboratory assessments will use local laboratories with results reported on the CRF. As such, laboratory assessments will be summarized by the visit in which the assessment was conducted.

For by-visit summaries, visit windowing will be implemented as specified in Section 4.10.1.3. For across visit summaries (e.g., worst post-baseline value), scheduled, unscheduled and repeat assessments will be considered.

All laboratory tests with values considered clinically significantly abnormal during participation in the study or within 30 days after the last dose of study intervention should be repeated until the values return to normal or baseline or are no longer considered clinically significant by the investigator or medical monitor. When there are repeat laboratory tests conducted on samples collected during the same visit, the last non-missing assessment will be summarized.

Laboratory values for hematology and clinical chemistry will be summarized as raw, change from baseline, and maximum change from baseline (for the participant). Descriptive statistics (for non-categorical data) will be presented by line of therapy for both raw values (n, mean, standard deviation, median, minimum, maximum) and changes from baseline.

A summary of the incidence of abnormal, high, or low values will be created by line of therapy and visit. Shift tables will be created for hematology and clinical chemistry parameters for which normal ranges exist. Shift tables for CTCAE grade shifts from baseline to worst post-baseline will also be presented by line of therapy for hematology and clinical chemistry for low and high shifts separately.

For urinalysis, a summary of the incidence of abnormal, high, and low values will be created. Shift tables will not be created for urinalysis.

A separate summary of findings of potential drug induced liver injury (DILI) will be prepared. The number and proportion of participants meeting one or both of the following criteria at any post-treatment visit will be summarized:

- ALT or AST $3 \times$ ULN and total bilirubin $2 \times$ ULN ($> 35\%$ direct bilirubin) or
- ALT or AST $3 \times$ ULN and international normalized ratio (INR) > 1.5 .

A figure for evaluation of Drug-Induced Serious Hepatotoxicity (eDISH) will also be presented.

By-participant listings of all laboratory data will be provided, with treatment-emergent abnormal values identified (as appropriate), and including center, participant identifier, line of therapy, age, sex, race, and visit. The lab normal ranges will also be included, where available. Laboratory values summarized for a given visit will be labeled with the visit number and all other laboratory data will be listed as unscheduled.

All values outside the clinical reference ranges will be flagged in the data listings. The abnormal values will be flagged with 'L' for values below the lower limit of the clinical reference range and 'H' for values above the upper limit of the clinical reference range and included in the listings. The Investigator will assess whether the values outside the clinical reference range are clinically significant and these will be reported as abnormal not clinically significant (NCS) or abnormal clinically significant (CS). Clinically significant laboratory values will be recorded by the Investigator as AEs.

